10.19 Daily Spasm Count

The 7-day average daily spasm count will be derived for each patient using the number of spasms recorded in the eDiary during the last 7 days preceding Period 1 Day 1 H0 (Baseline), and Day 15 and Day 21 of each treatment period as follow:

$$\frac{\text{Total spasm count during the 7 - day period}}{\text{Number of days in which the daily diary was completed during the 7 - day period}}$$

For each analysis timepoint, the 7-day average daily spasm count will be set to missing if spasm counts are not collected during 4 days or more in total or for 3 consecutive days during the 7-day period.

In case of the diary data are available but the visit does not take place the target visit date will be used.

On-treatment / off-treatment assessment

A 7-days average daily spasm count will be considered on-treatment if derived using only post-baseline daily records collected on or before the date of IMP discontinuation and will be considered off-treatment otherwise.

In case of IMP discontinuation, if possible with regards to missing data rule specified just above, the 7-day average daily spasm count considered on-treatment will also be derived using only post- baseline spasm counts collected on or before the date of IMP discontinuation.

Missing daily spasm count information

If for a given day, the spasm count is missing whereas the eDiary has been filled by the patient, the number of spasms will be imputed to "0" to derive the 7-days average daily spasm count.

The change from baseline will then be calculated (as respectively described in [Section 10.3](#)).

10.20 Multiple Sclerosis Spasticity Scale (MSSS-88)

The MSSS-88 will be completed at Day 21 of each period, and 8 sub-scales representing 8 domains along with a total score will be derived by summing each of the constitutive items provided that at least 50% of the items are answered. Missing responses will be replaced by the mean score of the items completed.

The questions will be grouped as follows:

- 3 spasticity specific symptoms
 - Muscle Stiffness: sum of questions 1 to 12,
 - Pain and Discomfort: sum of questions 13 to 21,
 - Muscle Spasms: sum of questions 22 to 35,
- 3 areas of physical functioning
 - Activity of Daily living (ADL): sum of questions 36 to 46,
 - Ability to Walk: sum of questions 47 to 56,
 - Body Movement: sum of questions 57 to 67,
- 2 area of psychosocial impact
 - Emotional health: sum of questions 68 to 80,
 - Social Functioning: sum of questions 81 to 88,
- Total score
 - Sum of the 8 non-missing subscales after missing data rule has been applied for each subscale, otherwise set to missing if any of the sub-scales is missing.

Table 10.20-1 Multiple Sclerosis Spasticity Scale - Missing Data Handling

Subscale and total score	Number of questions included in subscale and total score	Minimum number of questions required for score derivation (at least 50%)
Muscle Stiffness	12	6
Pain and Discomfort	9	5
Muscle Spasms	14	7
Activity of Daily living	11	6
Ability to Walk	10	5
Body Movement	11	6
Emotional health	13	7
Social Functioning	8	4

10.21 Adverse Events

10.21.1 Start and Stop Date Imputation

Table 10.21-1 Imputation Rules for Partial Adverse Events Start/Stop Dates

Parameter	Missing	Additional Conditions	Imputation
Start date for AEs	D	M and Y same as M and Y of first dose of study drug	Date of first dose of study drug
		M and/or Y not same as date of first dose of study drug	First day of month but should fall after 1st study drug intake or if impossible after informed consent date
	D and M	Y same as Y of first dose of study drug intake during period 1 and 2	Date of first dose of study drug
		Y after Y of first dose of study intake during Period 1 but same Y as 1 st study drug intake during Period 2	Date of first drug intake during period 2
		Y prior to Y of first dose of study drug but same as Y of informed consent date	Date of informed consent
		Y after Y of last study drug intake	The earliest date between date of last study drug intake + 14 days and end of study date
	D, M, Y	Not allowed by the system	Not applicable
Stop date for AEs	D	M and Y same as M and Y of last dose of study drug	The earliest date between date of last dose of study drug and end of study date
		M and/or Y not same as date of last dose of study drug	The earliest date between last day of month and end of study date
	D and M	Not allowed by the system	Not applicable
	D, M, Y	Not allowed by the system	Not applicable

AE = Adverse events; D = day; M = month; Y = year

Note: In all cases, if an estimated start date is after a complete stop date, use the first day of the stop date month. Similarly, if the estimated stop date is before a complete or imputed start date, use the last day of the start day month.

10.21.2 COVID-19 AE

A confirmed or suspected COVID-19 AE will be any adverse event for which the AE term or the preferred term include the character “COVID-19” but should not be “COVID-19 ELISA test negative”.

For instance, confirmed COVID-19 TEAE will be reported as:

- COVID-19 infection,
- COVID-19 disease,
- COVID-19 pneumonia,
- COVID-19 respiratory infection,
- Asymptomatic COVID-19,

whereas suspected COVID-19 AE will be coded as Suspected COVID-19.

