12.5.5 Exploratory Efficacy Analysis

All exploratory efficacy analyses will be conducted among the full analysis set during the 51-day efficacy randomized period.

If more than 20% of patients from FAS are excluded in the PP Analysis Set; the analyses may be repeated using the PP analysis set as described in [Section 12.5](#).

The exploratory efficacy analyses based on LLMT-10 are described in [Section 12.5.5](#).

If at least 5 patients have at least one visit where the studied endpoint is impacted by the COVID-19, as assessed by the investigator, the analysis of that endpoint will be repeated excluding the concerned patients as described below:

- For the average 25-foot walk time (as described in [Section 10.2](#) and in [Section 10.17](#)) if during Period 1 and/or Period 2, Day 21 visit, T25FW trials are impacted by COVID-19,

- For the 7-day average NRS spasticity score (as described in [Section 10.2](#) and in [Section 10.18](#)) if during Period 1 and/or Period 2, Day 15 or Day 21 visits are impacted by COVID-19 and patient is infected*,
- For the 7-days average daily spasm counts (as described in [Section 10.2](#) and in [Section 10.19](#)) if during Period 1 and/or Period 2, Day 15 or Day 21 visits are impacted by COVID-19 and patient is infected*,
- For MSSS-88 total and sub-scales scores (as described in [Section 10.20](#)) if during Period 1 and/or Period 2 at Day 21 Visit MSSS-88 scoring is impacted by COVID-19.

* For eDiary endpoints, impact on COVID-19 is assessed based on information collected on the “Visit COVID-19 Impact” eCRF form. Thus if reason is due to “Caregiver or family member infected with COVID-19” but not to “Patient infected by COVID-19” the assessment will not be discarded.

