12.7.1.1 Overall Adverse Event Summary

An overall adverse event summary will provide, by treatment arm, the number and percentage of patients with at least:

- One TEAE,
- One TEAE related to IMP,
- One confirmed or suspected COVID-19 TEAE (as defined in [Section 10.21.2](#)),
- One TEAE leading to permanent IMP discontinuation,
- One TEAE related to IMP leading to permanent IMP discontinuation,
- One serious TEAE,
- One serious TEAE related to IMP,
- One TEAE with outcome of death,
- One AE with outcome of death related to IMP,
- One TEAE of special interest.

This table will also present the number of TEAEs and the number of TEAE of special interest by treatment arm.

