Appendix 13.3 Enlarged lymph nodes of at least 2 sites

Search for PT including the word “Lymphadenopathy” alone or as part of another PT

Such as some examples are given below:

- Lymphadenopathy Mediastinal
- Paratracheal Generalized
- Retroperitoneal
- Vaccination site

Search for other PT that could reflect lymphadenopathy

- Benign lymph node neoplasm
- Lymph node palpable
- Lymph node scan abnormal

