7.0 Statistical Methods

The abbreviated reporting will follow the strategy as detailed in **Table 3.2-1**.

Table 3.2-1 Strategy for abbreviated reporting

Hierarchy	GWSP20105	
Primary	LLMT-6	Inferential and descriptive statistics; no supplementary, no subgroup analyses and no imputations for missing data
Secondary	LLMT-4	As established in study SAP to support safety assessment of Nabiximols as a globally marketed product
	TEAEs	
	Vital signs	
	Labs	
	ECG	
	C-SSRS	
Exploratory	PK	No processing, analyses, or reporting
	T25FW	Data cleaning for inclusion in listings; no descriptive or inferential statistics
	NRS spasticity	
	Daily spasm count	
	MSSS-88	

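### The COVID-19 adverse-event rule in SAP 10.21.2 also counts events whose term names COVID-19 vaccination or a negative COVID-19 test other than the one excluded

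*SAP*

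**What the plan says.** SAP 10.21.2 gives the rule: "A confirmed or suspected COVID-19 AE will be any adverse event for which the AE term or the preferred term include the character" string COVID-19. There is one exception, the term "COVID-19 ELISA test negative".

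Examples follow, introduced by "For instance, confirmed COVID-19 TEAE will be reported as". They cover infection, disease, pneumonia, respiratory infection and asymptomatic COVID-19. The section then adds: "whereas suspected COVID-19 AE will be coded as Suspected COVID-19".

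SAP 12.7.1.1 uses the definition for one line of the overall adverse event summary, a number and percentage of patients by treatment arm: "One confirmed or suspected COVID-19 TEAE (as defined in" Section 10.21.2).

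The SAP addendum written after early termination (7.0 Statistical Methods) lists TEAEs among the items in its strategy table. The entry that appears to govern them is "As established in study SAP to support safety assessment of Nabiximols as a globally marketed product". The table layout is broken in the text available, but on the natural reading the row is still to be produced.

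**The concern.** The row is meant to show how many patients had COVID-19, confirmed or suspected, while on each treatment. The rule finds mentions of COVID-19, which is a wider class. The single exclusion shows that the authors knew a text match picks up non-cases, but it closes only one route.

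Two kinds of non-case remain in plain view: reactions attributed to a COVID-19 vaccine, and negative tests other than the ELISA. Such verbatims are plausible here. Protocol 12.6 (A) accepts wording that ties a symptom to its cause, and Protocol 12.5 encourages investigators to say what they think caused an event.

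At stake is the meaning of one safety row. It combines confirmed and suspected cases in one count, so a reader of the table alone cannot separate illness from a vaccine reaction.

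**Working it through.** No sample size, power or error rate enters this point, and the plan states no figure to reproduce. The check is to apply the rule literally.

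**Rule as coded.** Flag the event if the string COVID-19 is in the AE term or in the preferred term, unless either term is the excluded one.

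**Result on eight made-up events.** The terms are illustrations, not trial data.

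| AE term | Preferred term | Illness meant? | Flagged? |
|---|---|---|---|
| COVID-19 infection | COVID-19 | yes | yes |
| Suspected COVID-19 | Suspected COVID-19 | yes | yes |
| COVID-19 ELISA test negative | (any other) | no | no |
| Sore arm after COVID-19 vaccine | Vaccination site pain | no | **yes** |
| Fever due to COVID-19 vaccination | Pyrexia | no | **yes** |
| COVID-19 PCR test negative | (any other) | no | **yes** |
| Sore arm after vaccine | Vaccination site pain | no | no |
| Covid vaccine reaction | Vaccination complication | no | no |

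Five of the eight are flagged, and three of those five are not illness. In the two vaccine cases the preferred term does not contain the string. The AE term alone triggers the flag, because the two fields are joined by *or*.

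The last two rows mark the limit of the problem: a vaccine reaction is caught only if one of its terms contains the exact string. By the same reading, a term recording contact with a COVID-19 case but no infection would be flagged.

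**Do the examples narrow the rule?** No. They are introduced as instances, so they show what was intended without closing the list. Neither document has a vaccination exclusion.

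**How far does it reach?** The row counts patients with at least one qualifying event. A misclassified event changes the row only if that patient has no true COVID-19 event in the same arm. It then adds one patient, or 100/N percentage points, where N is the number of patients exposed in that arm. The documents do not give N, since the addendum (6.0) says enrolment stopped before the planned number was reached.

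**What does not use the rule:**
- *Primary analysis.* The COVID-19 indicators in SAP 12.5.2.1.2 are built from scores or visits affected and from withdrawal due to COVID-19.
- *MAS supplementary analysis.* SAP 12.5.4.3.4 relies on the investigator's assessment of impact.
- *Diary endpoints.* In SAP 12.5.5, "impact on COVID-19 is assessed based on information collected on the “Visit COVID-19 Impact” eCRF form".
- *Total TEAE counts.* An event is a TEAE or not whatever its COVID-19 flag.

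**The case against.** The strongest reply is that searching both fields is a reasonable sensitive search and that little depends on it. Much of this stands.

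- **The two-field search has a purpose.** A true case recorded as *fever due to COVID-19* might be coded to a symptom preferred term and be found only through the verbatim. A flag built from preferred terms alone could lose it. This argues against replacing the method, but not against adding exclusions.
- **The error can be traced.** SAP 12.7.1.2 tabulates TEAEs by system organ class and preferred term, and the listings in SAP 12.7.1 show the investigator term beside the preferred term. A careful reader could recount.
- **No direction of bias is apparent.** Treatment is double-blind in a crossover, and nothing suggests that vaccine-related wording would favour one arm.

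Three stronger readings are tempting, and the documents do not support them:

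- *That vaccine reactions in general are tabulated as COVID-19.* Only those whose term contains the exact string are.
- *That a number of affected patients can be given by applying vaccination and reaction rates to the planned 190.* The documents give no such rates, and the trial stopped short of its planned enrolment. For the same reason, nothing shows that vaccine reactions would dominate the row.
- *That Appendix 13.3 shows COVID-19 vaccination events were anticipated.* Its "Vaccination site" entry is one example in a general lymphadenopathy search and does not contain the string.

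What survives is that the stated rule, followed exactly, puts some non-cases into a row labelled as cases.

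**Conclusion.** The point holds, at low severity. It concerns a stated rule that misclassifies certain terms, not a missing detail. Any event whose AE term or preferred term names COVID-19 vaccination, or a negative COVID-19 test other than the ELISA term, meets the definition of confirmed or suspected COVID-19.

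The effect is confined to one descriptive row of the overall adverse event summary. Its size cannot be stated, because the documents do not show whether any such event was reported. If none was, the row is correct as it stands.

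The conclusion rests on two assumptions: that the programmer applies SAP 10.21.2 as written, with no unwritten screening of hits, and that the addendum keeps the overall summary, as its table appears to say. It does not bear on the efficacy results or on the total number of TEAEs.

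**What to change.** Keep the search of both the AE term and the preferred term. Replace the single exclusion with three classes: any hit that denotes vaccination or immunisation, exposure without infection, or a negative COVID-19 test of any kind. Have the remaining hits reviewed by someone blinded to treatment, and settle the list before unblinding.

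The cost is a sentence or two in SAP 10.21.2, or in the addendum, and a brief manual review. No data collection, coding or other table changes. If the rule is left as it is, a footnote should say that the row is a text-match count, and the contributing events should be listed with their investigator terms.

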10.21.3 Time to First Onset of AE

The time to first onset of AE will be defined by study period as:

- AE start date – IMP start date in the studied period

For AEs with an onset date occurring during the 21-days on-treatment safety Period 1 (as defined in [Section 10.1.1](#)) the IMP start date refers to the date of 1st IMP spray intake during Period 1.

For AEs with onset date occurring during the 21-days on-treatment safety Period 2 (as defined in [Section 10.1.1](#)), the IMP start date refers to Period 2 start date provided that the patient is exposed during Period 2.

Based on the above value time to first onset of AE will be categorized as:

- 1-7 days,
- 8 to 14 days,
- 15 to 21 days,
- >21 days.

If onset time is shorter as 1 day, it will be included in the 1-7 days category.

For the purpose of time-to-event analysis, censoring rules are defined in [Section 12.7.2.3](#).

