10.1.2 Reference Day and Study Day

The reference day (Day 1) will be the day of the first dose of study drug administration.

For a patient who was randomized but not exposed, the reference day date will be imputed by the randomization date.

The reference day for Period 1 (Period 1 Day 1) will be the reference day.

The reference day for Period 2 (Period 2 Day 1) will be the first day of IMP administration during Period 2. For a patient who entered the second period but was not exposed during this period, this reference day date will be imputed by the date of Visit 6 IRT call, if any, or the Visit 6 date.

The study day is defined relative to the reference day date. For assessments that occur after this visit date, the study day is calculated as (assessment date – reference day date + 1). For assessments that occur prior to first dose date, study day will be calculated as (assessment date – reference day date).

For the analyses being done by treatment arm, an **analysis day** will need to be derived for each treatment period as described in Table 10.1-1. The analysis day is defined relative to the date of reference day of each study period.

For assessments that occur prior to reference day date, analysis day will be calculated as (assessment date – reference day date);

For assessments that occur on or after the Period 1 reference day date until the end of the wash-out period, analysis day will be calculated as (assessment date – Period 1 reference day date +1);

For assessments that occur on or after Period 2 reference day date the analysis day will be calculated as (assessment date – Period 2 reference day date +1);

Thus, there is no study day or analysis day referring to Day 0.

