12.7.1 Adverse Events

Adverse events (AEs) will be coded using MedDRA 24.0 or higher according to the version in use at time of database lock. All safety analyses of AEs will be performed by actual treatment arm and reported using the Safety Analysis Set. An AE will be considered a TEAE if it first occurs or worsens in severity or seriousness after the first dose of IMP intake and before the last dose date + 15 days.

All AEs will be classified during the pre-treatment period, the 51-day safety on-treatment period or during the follow-up period as follows:

Events that occurred before first IMP intake without worsening or becoming serious after the first IMP dose are classified as **pre-treatment AEs**;

Events that occurred or worsens between first IMP dose and 14 days after IMP last dose are classified as on-treatment AE and are defined as **treatment-emergent AEs** (TEAEs);

- TEAE occurring during 21-day on-treatment safety Period 1 will be considered emergent to actual treatment received during Period 1 (as defined in [Section 10.1.1](#)).
- TEAE occurring during 21-day on-treatment safety Period 2 will be considered emergent to actual treatment received during Period 2 (as defined in [Section 10.1.1](#)).

Events occurring more than 15 days after last dose are classified as **follow-up AEs**.

Consequently, TEAEs will be summarized by treatment arm using the actual treatment received at each given period. Any adverse event occurring during the wash-out period will be linked to the actual treatment arm defined for Period 1, whereas any AEs occurring after last IMP dose will be linked to the actual arm defined at time of permanent study drug discontinuation.

The following events will not be identified as AEs in this study:

- Medical or surgical procedures (e.g., surgery, endoscopy, tooth extraction, etc.). The condition (the “triggering event”) that leads to the procedure are adverse events and will be reported as such.

- Pre-existing conditions present or detected prior to the first dose of study drug that do not worsen during the study.

Counting rules

For incidence reporting, if a patient reported more than one AE that was coded to the same preferred term/system organ class within a given treatment arm, the patient will be counted only once for that specific preferred term/system organ class by treatment arm and the rules defined below will be applied.

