12.7.1.2 All-causality Treatment-emergent Adverse Event Summary

Descriptive presentations of TEAEs will be given by PT and SOC for the Safety Analysis Set. The number and percentage of patients reporting at least one TEAE within a given treatment arm will be provided as described below

- *All TEAEs by SOC and PT,
- *All TEAEs by SOC, PT and subgroups (as described in [Table 12.7-1](#)),
- Most common TEAEs (incidence $\geq 5\%$ in either treatment arm) by SOC and PT,
- Most common TEAEs (incidence $\geq 2\%$ patients in either treatment arm) by SOC and PT,
- Most common TEAEs (incidence $\geq 2\%$ patients in either treatment arm) by SOC, and PT and subgroups (as described in [Table 12.7-1](#)),
- All TEAEs by SOC, PT and maximum severity,
- All TEAEs by SOC, PT and worst action taken on study drug,
- All TEAEs by SOC, PT and time of first onset of AE categorized as:
1-7 day, 8 to 14 days, 15 to 21 days and > 21 days (as described in [Section 10.21.3](#)),
- All TEAEs by SOC, PT and AE duration, categorized as:
1-7 day, 8 to 14 days, 15 to 28 days, 29 to 42 days ,43 to 61 days , > 61 days, ongoing, indeterminate (as described in [Section 10.21.4](#)),
- All TEAEs by SOC, PT and relationship to IMP,
- All treatment-related TEAEs by SOC and PT and maximum severity,
- *All treatment-related TEAEs by SOC and PT and subgroups (as described in [Table 12.7-1](#)),

- *All treatment-related TEAEs leading to permanent IMP discontinuation by SOC and PT,
- *All TEAEs leading to permanent IMP discontinuation by SOC and PT,
- *All TEAEs leading to permanent IMP discontinuation by SOC and PT and subgroups (as described in [Table 12.7-1](#)),
- All treatment-related TEAEs leading to permanent IMP discontinuation by SOC and PT and maximum severity,
- All non-serious TEAEs by SOC and PT,
- All most common non-serious TEAEs (incidence $\geq 5\%$ in either treatment arm) by SOC and PT.

**These tables will also present the total number of AEs by treatment arm and as appropriate by category of subgroup.*

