12.7.2.3 Adverse Events of Special Interest

An adverse events of special interest (AESI) is any adverse event of scientific or medical interest to the study medication. The types of AESIs which will be analyzed are presented in **Descriptive presentations of AESIs** will be given for each AESI category on the safety analysis set presenting:

- The number and percentage of patients with at least one treatment-emergent AESI,
- The number and percentage of patients with at least one treatment-emergent AESI by SOC and PT,
- The number and percentage of patients with at least one severe treatment-emergent AESI,

- The number and percentage of patient with at least one serious treatment-emergent AESI,
- The number of and percentage of patients with at least one treatment-emergent AESI leading to permanent IMP discontinuation,
- The number of treatment-emergent AESI,
- The number of severe treatment-emergent AESI,
- The number of serious treatment-emergent AESI,
- The number of treatment-emergent AESI leading to permanent IMP discontinuation,
- The number of unique* treatment-emergent AESI,
- The number of unique* severe treatment-emergent AESI,
- The number of unique* serious treatment-emergent AESI,
- The number of unique* treatment-emergent AESI leading to permanent IMP discontinuation,
- The time to first onset of treatment-emergent AESI categorized as :1-7 day, 8 to 14 days, 15 to 21 days, 21 to 28 days and > 28 days (as described in [Section 10.21.3](#)),

**Unique AESI is defined as any AESI coded with the same PT and having the same date of onset.*

Analysis of time to first onset of AESIs will be conducted by actual treatment arm on the Safety Analysis SAS using the SAS® LIFEEST procedure.

Assuming no carry over effect, Kaplan-Meier plots (estimates) of cumulative incidence of first onset of AESI will be provided by actual treatment arm on the Safety analysis set. The time to AESI onset (in days) is defined as the number of days from 1st IMP intake of the treatment arm (e.g., nabiximols, placebo) the AESI is emergent to (as defined in [Section 12.7.1](#)) until the onset of the AESI (see detailed in [Section 10.21.4](#)).

For patients not known to have experienced an AESI during respectively Period 1 and Period 2:

- Period 1 censoring day is the date of 1st IMP intake during Period 2 minus 1 day for those patients continuing in Period 2 and, the end of study date for those patients who discontinued before Period 2,

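### AE onset bins are one day out of step with the SAP's other day counts, the AESI bins overlap at day 21, and the TEAE and follow-up AE limits conflict at day +15

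*SAP*

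**What the plan says.** **Onset.** SAP 10.21.3 defines time to first onset as "AE start date – IMP start date in the studied period", with bins 1–7, 8–14, 15–21 and >21 days. It adds: "If onset time is shorter as 1 day, it will be included in the 1-7 days category". SAP 12.7.1.2 repeats the bins for all TEAEs: "1-7 day, 8 to 14 days, 15 to 21 days and > 21 days".

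**Other day counts.** SAP 10.1.2 adds 1 for study and analysis days and concludes that "there is no study day or analysis day referring to Day 0". Exposure duration (10.7) and AE duration (10.21.4) also add 1.

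**AESI bins.** SAP 12.7.2.3 cites 10.21.3 for its onset categories but lists, after 8–14, "15 to 21 days, 21 to 28 days and > 28 days". For the time-to-AESI analysis it points to 10.21.4, which is the AE duration section.

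**End of the TEAE window.** SAP 12.7.1 ends TEAEs 14 days after last dose (equivalently, before last dose + 15 days). It then says "Events occurring more than 15 days after last dose are classified as" follow-up AEs. SAP 10.1.1 extends the on-treatment safety period by 14 days for AEs and starts the follow-up period on the next day.

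**The concern.** Each rule places events in time categories, and each goes wrong at a boundary.

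- The onset rule puts an extra day into the first bin and moves every later bin one day along. The exposure categories in SAP 12.3.1.1 carry almost the same labels (Day 1 to 7, 8 to 14, 15 to 21) but rest on a duration that adds 1. Exposure and AE tables with matching labels would therefore describe different days. The onset tables also take as denominator the patients at risk in each interval (12.7.1), so the boundaries affect more than the numerators.
- An AESI with onset 21 belongs to two categories, and two sections with different day counts are cited for the same variable. A programmer has to guess.
- An event exactly 15 days after last dose has no class under 12.7.1, while 10.1.1 puts it in follow-up.

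The tables still matter after early termination. The 2023 addendum appears to keep TEAE reporting as set out in the SAP, and it does not amend these rules.

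**Working it through.** The plan gives no figure to reproduce. The check assigns each day to a class under the rules as written.

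**1. Onset bins (10.21.3).** Let d be the treatment day, with first dose on Day 1 (10.1.2). As written, onset = d − 1, and onset 0 goes to the first bin. With the study-day convention, onset = d.

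| Bin label | Onset values as written | Treatment days as written | Days in bin | Treatment days with +1 |
|---|---|---|---|---|
| 1–7 | 0–7 | 1–8 | 8 | 1–7 |
| 8–14 | 8–14 | 9–15 | 7 | 8–14 |
| 15–21 | 15–21 | 16–22 | 7 | 15–21 |
| >21 | 22 and above | 23 onward | open | 22 onward |

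The first three bins cover 8 + 7 + 7 = 22 days. At a constant event rate (an illustrative assumption) the shares are:

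- 8/22 = 36%
- 7/22 = 32%
- 7/22 = 32%

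The step from the first bin to the second is 1 − 7/8 = 12.5%, after which the profile is flat. With +1, each of the three bins holds 7 days and 1/3 of events.

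**2. AESI bins (12.7.2.3).** The bins are 1–7 (with onset 0 added), 8–14, 15–21, 21–28 and >28. Every whole-day value falls in exactly one bin except 21, which falls in both 15–21 and 21–28. Section 10.21.3 has no 21–28 or >28 bin. Section 10.21.4, cited for the time-to-event version, computes stop date − start date + 1, which is not an onset time.

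**3. Days after last dose.**

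| Days after last dose | 12.7.1 | 10.1.1 (14-day extension) |
|---|---|---|
| 14 | TEAE | on-treatment safety period |
| 15 | no class | follow-up period |
| 16 | follow-up AE | follow-up period |

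**4. Who can reach day +15.** AEs are collected up to Visit 10, which is 7 (+3) days after the later of last dose and Visit 9 (Protocol 9.1.5, 12.1.1).

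- A completer takes the last dose on the day of Visit 9, so Visit 10 falls at most 7 + 3 = 10 days later. Day +15 is out of reach.
- A patient who stops IMP early and stays to the end of the period has Visit 9 at nominal period Day 21 and Visit 10 at Day 28 to 31. With last dose on Day L, the requirement is L + 15 ≤ 28, so L ≤ 13; or L + 15 ≤ 31, so L ≤ 16.

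**The case against.** **Elapsed days are a legitimate measure.** Time since first dose need not add 1. SAP 12.7.2.3 reports Kaplan-Meier estimates at 7, 14, 21 and 28 days after first intake, and Protocol 9.1.2.2 describes Visit 3 on Day 8 as 7 days after first dose. Bins ending at elapsed days 7, 14 and 21 fit those points, and the onset-0 rule is explicit and reproducible. This stands as a defence of the subtraction. It does not defend an 8-day bin labelled 1–7 beside exposure categories with similar labels on another count. The onset-0 rule creates the 8-day bin; it does not correct it.

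**The overlap at 21 looks like a typing slip.** That is plausible: 10.21.4 has a similar one in its duration bins (15–28, then 28–42), which 12.7.1.2 prints as 29–42. The AESI bins have no second listing that settles the matter. Finer bins for AESIs are not an error in themselves, but the mismatch with the cited section needs a sentence.

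**Section 10.1.1 already decides day +15.** It does, and this stands. What remains is a conflict of wording with 12.7.1, of small reach.

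**Stronger readings that a reader might infer.** One is that the third bin holds only 6 days, so that a constant rate would show a false fall of 1 − 6/8 = 25% from the first bin to the third. That requires counting to stop at Day 21, the last dosing day. The safety period continues into washout or to 14 days after last dose (10.1.1), and washout events are attributed to the Period 1 treatment (12.7.1), so Day 22 is in the bin and it holds 7 days. Another is that the onset tables are meant to separate titration from maintenance. Neither 10.21.3 nor 12.7.1.2 says so. SAP 10.8.1 bounds those phases by the actual dates of Visits 4 and 8, which have a ±1 day window, so fixed bins would not match them even with +1.

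**Conclusion.** The point holds with small reach. The first onset bin spans 8 treatment days, and the following bins sit one day later than the SAP's study-day, exposure and AE-duration counts imply. The distortion is 36%/32%/32% against equal thirds, assuming a constant event rate over Days 1–22. Onset 21 is counted in two AESI bins, and the AESI analysis cites the wrong section for its time variable. An event on day +15 has no class in 12.7.1 but is follow-up under 10.1.1; only patients who stop IMP early can have one, with last dose by about Day 13, or Day 16 if Visit 10 uses its full window (Visit 9 on nominal Day 21).

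The consequences are limited to descriptive safety tables. No efficacy result or sample-size figure changes. The documents do not support a 6-day third bin, a 25% decline, or a stated aim of separating titration from maintenance. That the TEAE tables are still to be produced rests on reading the addendum's reporting table as retaining them.

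**What to change.** 1. **SAP 10.21.3:** define categorical onset as AE start date − first dose date in the period + 1, and delete the rule for onset below 1 day. The first three bins then equal treatment Days 1–7, 8–14 and 15–21.
2. **SAP 12.7.2.3:** make the later AESI bins 15–21, 22–28 and >28. Either use one set of bins in 10.21.3, 12.7.1.2 and 12.7.2.3, or state that the AESI set splits the >21 bin. Changing 10.21.3 and 12.7.2.3 alone would leave 12.7.1.2 inconsistent.
3. **SAP 12.7.2.3:** change the cross-reference for time to AESI onset from 10.21.4 to 10.21.3, and state that the Kaplan-Meier time points use the same day count as the bins.
4. **SAP 12.7.1:** define follow-up AEs as more than 14 days after last dose, matching 10.1.1.

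The cost is a few lines across four SAP sections and the matching program changes. No new data are needed.
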